## 12.8 **Notification of Deaths**

If the research team become aware of the death of a participant (whether related to the trial or not) this should be notified to the LCTC using the database **within 24 hours** of becoming aware, preventing any further contact with the bereaved family.

## 12.9 **Reporting Procedures**

Due to the nature of the trial and the intervention, adverse events will not routinely be reported. The occurrence of a safety event that is serious and related may come to the attention of research staff during routine study visits, from the participant's notes, directly from the participant or by other means. Any questions concerning adverse event reporting should be directed to the LCTC in the first instance. A flowchart is given in section 12.10 below to aid in determining reporting procedures for different types of adverse events.

### 12.9.1 Related Serious Adverse Events

Related SAEs should be reported to the LCTC within 24 hours of the local site becoming aware of the event using the SAE eCRF form. The SAE form asks for the nature of the event, date of onset, severity, corrective therapies given, outcome and causality. The reporting dentist should assign the causality of the event. Additional information should be provided within 5 days if the event has not resolved at the time of reporting. As a minimum, the SAE form should contain the following information:

Minimum information required from site	Corresponding data/information
Valid registration number and Sponsor study number	ISRCTN number and sponsor study number
One identifiable coded subject	Patient study number
One identifiable reported	Study site number
	Reporting site research team member (PI/delegate)
One related serious safety event	Description of the event, including date of onset
	The reason why the event is classed as serious
One suspect intervention	The CHOICE intervention
A causality assessment	Investigator assessment of causality

Once reported to the LCTC, the CI (or delegated other) will be asked to review the event and provide their opinion on expectedness. Any Related and Unexpected Serious Adverse Events (RUSAEs) must be emailed to the REC by LCTC using the HRA non-CTIMP safety report to REC form. These must be sent within 15 days of LCTC becoming aware of the event. All dentists will be informed of all RUSAEs occurring throughout the trial. Local dentists should report any RUSAEs as required locally.

When reporting related SAEs, the reporting dentist should apply the following criteria to provide information relating to event outcomes: resolved; resolved with sequelae (specifying with additional narrative); not resolved/ongoing; ongoing at final follow-up; fatal or unknown.

### 12.9.2 Follow up of related Serious Adverse Events

Related SAEs should be subsequently followed up in line with the processes below:

- Follow up must continue until clinical recovery is complete or until the event has stabilised. **N.B**. Follow up may continue after completion of protocol treatment if necessary.
- Follow up information is to be entered on to the SAE eCRF
- The appropriate box on the SAE eCRF must be ticked to identify the type of report; this is dependent on the resolution status of the SAE e.g. follow up/final.

# 12.10 Flowchart for Site Reporting Requirements of Adverse Events

## 12.11 Investigator Reporting Responsibilities

The PI is responsible for ensuring that all safety events requiring recording on this study which the local research team becomes aware of are reported to LCTC. It is the responsibility of the PI/Co-PI as recorded on the Delegation Log (medically qualified person) to assess the seriousness and causality of events. When documenting any adverse events the correct medical terminology must be used.

Safety events which meet the definition of "serious" and related (possibly, probably or almost certainly) must be reported in more detail to the LCTC on the SAE eCRF form and must be reported **immediately and in no circumstances later than 24 hours from becoming aware** where they will be appropriately processed.

The SAE eCRF form should be completed by an appropriately delegated member of the research team; the assessments of seriousness and causality must be performed by an appropriately medically qualified and delegated person/dentist. Minimum reporting information must be provided in initial reports for all studies (see section 12.9.1).

Safety events should be reported by the site in accordance with local policy.

### 12.11.1 **Reporting an initial or follow-up SAE**

The Investigator should ensure the actions below are completed for all reportable SAEs:

- 1) The related SAE should be entered on to the SAE eCRF form on the trial database within 24 hours of becoming aware of the event.
- 2) When submitting a SAE to the LCTC, the reporter should also telephone the LCTC to advise that a SAE report has been submitted as soon as possible.
- 3) The responsible investigator must notify their Practice Manager of the event (as per standard local governance procedures).
- 4) The patient must be identified by trial number, age at time of onset and initials **only**. The patient's name **should not** be used on any correspondence.
- 5) SAEs must be subsequently followed up in line with the processes documented in section 12.9.2.

### 12.11.2 Backup SAE reporting

In the event of a problem with the trial database (power failure, server failure etc), a backup SAE form will be made available.

Patient safety incidents that take place in the course of research should be reported to the National Reporting and Learning System (NRLS) by each participating NHS Trust in accordance with local reporting procedures.

## 12.12 LCTC Responsibilities

The trial Sponsor, Queen's University Belfast, have delegated to LCTC the duty of onward reporting of safety events to REC. SOPs will be followed to ensure appropriate reporting as detailed below.

All related "serious" adverse events will be forwarded to the Chief Investigator (or delegated other) by LCTC within 24 hours of receiving the minimum information from site. The CI (or delegated other) will review information provided by site and for all events assessed as "related" will provide an assessment of "expectedness".

Safety events which are assessed as "serious", "related" and "unexpected" (i.e. RUSAEs), will be onward reported by LCTC to the ethics committee **within 15 days** of the LCTC first becoming aware of the event.

Additionally, RUSAEs will be reported to the trial Sponsor(s) and Principal Investigators of participating sites.

A list of all safety events recorded for the trial will also be reported annually by LCTC to the ethics committee and Independent Data Safety & Monitoring Committee.

Any concerns raised by the TSC/IDSMC or inconsistencies regarding safety reporting noted at a given site may prompt additional training at sites, with the potential for the LCTC to carry out site visits if there is suspicion of unreported related SAEs. Additional training will also be provided if there are unacceptable delays in safety reporting timelines.

## 12.12.1 Safety Reports

Safety reports will be generated during the course of the trial which allows for monitoring of safety events including reporting rates and safety events by site. The LCTC will send Annual Progress Reports (APRs) containing a list of all reported RUSAEs to the main REC. If any safety reports identify issues that have implications for the safety of trial participants, the PIs at all institutions participating in the trial will be notified.

### 12.12.2 Urgent Safety Measures (USMs)

An urgent safety measure (USM) is a procedure to protect clinical trial participants from any immediate hazard to their health and safety but has not previously been defined by the protocol. It can be put in place prior to authorisation by the REC.

The LCTC will notify the REC immediately and, in any event, within 3 days that such a measure has been taken and the reasons why it has been taken. The initial notification to the REC will be by telephone (ideally within 24 hours) and a notice in writing will be sent within 3 days, setting out the reasons for the USM and the plan for further action. After discussion with the REC, further action will be agreed, which may include submission of a substantial amendment, a temporary halt, or permanent termination of the trial.

Following notification, if a substantial amendment is required this must be submitted as soon as possible to the REC. If the study is temporarily halted it may not recommence until authorised to do so by the REC. If the study is permanently terminated before the date specified for its conclusion (in the original applications to REC), the Sponsor should notify the REC within 15 days of the date of termination by submitting the formal End of Trial Notification.

## 12.13 Contact Details and Out-of-hours Medical Cover

Due to the type of intervention, emergency and out-of-hours medical care will be in line with usual NHS arrangements and local standard practice; no special provision is required for CHOICE participants. All participants will be provided with a copy of the information sheet which includes information about their participation and contact details for the local CHOICE trained staff who may be contacted if necessary. During office hours, the CI or delegate are able to provide advice in relation to participation using the contact details listed at the beginning of this document.

# **13 STATISTICAL CONSIDERATIONS**

## 13.1 Introduction

A full detailed Statistical Analysis Plan (SAP) and Health Economics Analysis Plan (HEAP) will be developed prior to the analysis of the main trial. The main features of these planned statistical analyses are included here in the protocol.

## 13.2 Sample Size

## 13.2.1 Sample Size Calculation

In the clinical trial evaluating the DR-BNI technology in secondary care, the Dental RECUR trial, 62% of children in the control group developed new caries, compared to 44% in the test group, a difference of 18 percentage points. An inclusion criterion for that trial was that the child was scheduled to have at least one primary tooth extracted. The children in the sample achieved had a median of 5 teeth extracted. In addition to the high levels of dental caries experience, the children were aged between 5 and 7 years at recruitment. The children eligible to join the CHOICE trial will have at least one decayed tooth but we will exclude those whose disease is so advanced that they require dental extractions. This is a critical distinction, as one of the objectives of the CHOICE trial is to determine whether earlier intervention in the disease process using DR-BNI can reduce the number of children needing dental extractions; as well as reduce the number having restorations for caries, so further reducing the cost of care to the NHS. The CHOICE trial will also include children at a younger age, from 3 to 7 years, rather than from 5 to 7 years. Therefore, there is potential for a smaller difference to be clinically important achieving a longer-term benefit. These differences in the sample composition mean that it is important to power the trial to detect a smaller difference than found in the RECUR trial, as this difference will be clinically important. Therefore, the CHOICE trial has been powered to detect a clinically significant difference of 12 percentage points.

To give 90% power, with  $\alpha$ =0.05, requires 363 participants per group. Allowing for 20% loss to follow-up, we will aim to recruit 454 participants per group, 908 in total. We will provide each of the 4 regions with a recruitment target of 227. Each region aims to recruit 10 dental practices, resulting in an achieved sample size target per practice of 22-23 patients over an 18-month recruitment period.

## 13.2.2 Feasibility of Sample Size

Included in the Site Suitability Assessment Form to be completed by each dental practice wishing to become a site for the CHOICE trial, the lead practitioner is asked to estimate the number of children seen who could meet the eligibility criteria. Only those practices that see sufficient child patients will be deemed suitable. Therefore, feasibility to recruitment will be considered from the outset.

It is recognised that patient profiles attending the sites do not directly equate with recruitment and the research team has already recognised the challenge of recruitment of suitable patients in primary dental care, as those children with dental disease are more likely to be irregular attenders. Therefore, a study within a trial (SWAT) is planned to support recruitment as described in Section 11. In addition, review of the literature has shown that close monitoring of accruals can help identify recruitment challenges early. Further, in this study, a regional dental lead is a member of the research team in each part of the UK participating. The four regional dental leads will support sites in getting recruitment moving forward and help identify challenges. These aspects will be discussed at Trial Management Group meetings to identify if there are common issues which could benefit from a simple protocol amendment to support recruitment.

Planned recruitment strategies include the delivery of a motivational letter and oral health toolkit intervention to promote the trial amongst irregular-attending children (as part of the SWAT) and the provision of recruitment posters to the CHOICE dental practices.

Retention strategies include the development of an online 'Parent Hub' where participants can receive updates about the progress of the trial and reminders for follow-up visits. In addition, multiple methods for contacting participants will be collected, including postal and email addresses and telephone numbers.

# 13.3 Method of Randomisation

### 13.3.1 Allocation Sequence Generation

Participants will be equally randomised to the intervention or control group in a 1:1 ratio using a secure (24-hour) web-based randomisation program controlled centrally by LCTC. Randomisation lists will be generated using block randomisation with random variable block length, stratified by site and age. The lists will be produced by an independent statistician (who is not otherwise involved in the CHOICE trial) at LCTC.

### 13.3.2 **Concealment and Implementation of Allocation Sequence**

Patient allocations will be irrevocably generated upon completion of the web-based randomisation form by a delegated member of the trial research team. Allocation concealment will be ensured as the service will not release the randomisation code until the patient has been recruited into the trial; this takes place after all baseline measurements have been completed.

## 13.4 Blinding Considerations

The assessors collecting outcomes at 24 months will be blinded to treatment allocation. If accidental unblinding occurs, this will be reported to the LCTC. Trial teams at the dental practice and participants will not be blinded.

## 13.5 **Interim Analyses**

Analyses of the accumulating data will be performed at regular intervals (at least annually) for review by an IDSMC. These analyses will be performed at the LCTC. The IDSMC will be asked to give advice on whether the accumulated data from the trial, together with results from other relevant trials, justifies continuing recruitment of further patients or further follow-up. A decision to discontinue recruitment, in all patients or in selected subgroups will be made only if the result is likely to convince a broad range of clinicians including participants in the trial and the general clinical community.

The first six months of recruitment will form an internal pilot, with prespecified progression criteria, which will be reviewed by the IDSMC and TSC. The criteria are based on trial recruitment and receipt of the intervention, and the progression criteria are shown in the table below.

	Red	Amber	Green
Percentage of participants	<90%	≥90%	100%
randomised to the			
intervention group who			
received the intervention			
Recruitment	<70% of target	≥70% of target	≥100% of target
rate/site/month			
Number of sites opened	<70% of target	≥70% of target	≥100% of target

If the criteria meet the green threshold, recruitment will continue. If they fall into amber, we will consider strategies to improve rates. If they are red, then the possibility of ending the trial early will be discussed with the funders and oversight committees.

## 13.6 Analysis Plan

A full statistical analysis plan (SAP) will be written prior to the conduct of any comparative analysis of the treatment arms. The main features of the SAP are summarised below:

Participants will be included in the analysis set based on the intention-to-treat principle.

The primary outcome will be compared between groups using logistic regression, adjusted for site and baseline dental caries.

Count outcomes such as number of teeth developing caries, number of fillings and number of extractions will be compared using Poisson regression adjusted for site and baseline caries. Secondary parent reported outcomes will be analysed using linear or logistic regression, adjusted for site and baseline values.

The comparative outcomes in different ethnic groups will be explored by adding terms for ethnicity and interaction terms between ethnicity and treatment to the models of caries and oral health behaviour outcomes. This will be an exploratory analysis as we have not powered the trial to detect interactions.

An exploratory analysis will be carried out to investigate the potential mediating effects of parental self-efficacy and relief/regret on the effect of the intervention on the clinical outcome. This analysis will test for partial mediation using a series of regression analyses. We will conclude that mediation is present if the four statements below are true:

- 1. The total of effect of DR-BNI on caries is significant
- 2. The effect of DR-BNI on the mediating variable is significant
- 3. The effect of the mediating variable on caries, adjusted for DR-BNI is significant
- 4. The direct of effect of DR-BNI on caries adjusted for the mediating variable is reduced from the effect modelled in step 1.

As much information as possible will be collected about the reasons for missing outcome data; this will be used to inform any imputation approaches employed in the analysis. Such methods will be fully described in the SAP.

In the treatment arm of the study, for each of the target behaviours (tooth brushing, and reducing sugary foods and drinks) exploratory analyses will be carried out to investigate the potential mediating effects of behavioural intention on the effect of both anticipated and experienced emotions on caries. These analyses will test for partial mediation using a series of regression analyses. If these analyses indicate an association between either of the experienced emotions (regret or relief) and clinical outcome, we will conduct further exploratory mediation analyses to determine whether any association is mediated by the anticipation of the same emotion i.e., whether an association between experienced relief and clinical outcome is mediated by anticipated relief, and whether an association between experienced regret and clinical outcome is mediated by anticipated regret.

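### Randomisation is stratified by site and age, but the stated primary, count and parent-reported models leave out age, which may give up a little power for no reason

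*Protocol*

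**What the plan says.** Section 13.3.1 specifies "block randomisation with random variable block length, stratified by site and age". Section 13.6 then lists covariates for three groups of outcomes:

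- Primary outcome: "The primary outcome will be compared between groups using logistic regression, adjusted for site and baseline dental caries".
- Counts (teeth developing caries, fillings, extractions): Poisson regression with site and baseline caries.
- Parent-reported outcomes: linear or logistic regression with site and baseline values.

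The exploratory models in the same section bring in ethnicity or mediators, again without age. The text is offered as the main features of a SAP to be written before any comparison of the arms. Section 10.4 lists the child's age among the baseline data, all of which are completed before randomisation.

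On size, Section 13.2.1 states that "the CHOICE trial has been powered to detect a clinically significant difference of 12 percentage points", and derives the number as follows: "To give 90% power" at a significance level of "0.05, requires 363 participants per group". It continues: "Allowing for 20% loss to follow-up, we will aim to recruit 454 participants per group, 908 in total".

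**The concern.** Stratifying on a factor balances it between the arms. If the factor also predicts the outcome and the model ignores it, the model's standard error takes no credit for that balance. The test then rejects less often than one that includes the factor, both under the null and under the alternative. The usual remedy is to carry every stratification factor into the analysis. Section 13.6 does so for site and not for age.

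There is reason to think age could matter here. Children enter from age 3 to just under 8 (Section 8.1), and the outcome counts disease in teeth that were sound or had not yet come through at entry (Section 6.2). Which teeth those are changes a good deal over that age range. Baseline caries records past disease and need not capture it. The protocol also chose age as a stratifier.

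At stake is a small amount of power in the primary comparison, and agreement between how the trial randomises and how it analyses.

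**Working it through.** **1. The plan's own sample size.** Inputs from Section 13.2.1: 90% power, alpha 0.05 (two-sided assumed, as the sidedness is not stated), a difference of 12 points, 20% loss. Section 13.3.1 gives 1:1 allocation. The control rate for CHOICE is not stated; the earlier trial is reported as "62% of children in the control group developed new caries, compared to 44% in the test group, a difference of 18 percentage points". Taking 56% v 44%, with pooled variance and no continuity correction:

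n = [1.960 × √(2 × 0.50 × 0.50) + 1.2816 × √(0.56 × 0.44 + 0.44 × 0.56)]² / 0.12²
= (1.3859 + 0.8996)² / 0.0144 ≈ 363 per group.

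The pair 55% v 43% also gives 363. Then 363 / 0.8 = 453.75, rounded up to 454, and 2 × 454 = 908. The stated figures reproduce. The formula uses no covariates, so they do not depend on whether age is in the model.

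**2. Stratification and models side by side.**

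| Item | Site | Age | Baseline |
|---|---|---|---|
| Randomisation (13.3.1) | yes | yes | – |
| Primary logistic (13.6) | yes | no | caries |
| Count models (13.6) | yes | no | caries |
| Parent-reported models (13.6) | yes | no | own baseline value |

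**3. Size of the effect, by simulation.** From the protocol: 908 children, 40 practices (4 regions × 10), 20% loss, 1:1 blocked allocation within site and age. Assumed, because the protocol gives no figure: two age bands split at 5 years, uniform ages, blocks of 2 or 4, loss at random, site SD 0.4 on the logit scale, baseline caries log-odds 0.4 per unit and mildly correlated with age, and a conditional treatment log odds ratio of −0.52. The test is the Wald test from logistic regression with site as fixed effects and baseline caries, with and without the age band. There were 6,000 runs per cell.

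| Assumed age-band odds ratio | Power without age | Power with age | Gain (points) | Null rejection without age | Null rejection with age |
|---|---|---|---|---|---|
| 1 | 91.9% | 92.0% | 0.0 | 6.2% | 6.2% |
| 1.5 | 91.8% | 92.0% | 0.2 | 5.1% | 5.4% |
| 2 | 89.9% | 90.8% | 0.8 | 5.7% | 6.0% |
| 3 | 89.5% | 90.8% | 1.4 | 5.7% | 6.1% |
| 4 | 86.8% | 88.7% | 1.9 | 5.1% | 5.6% |

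Gains are taken from unrounded values. The Monte Carlo standard error is √(0.05 × 0.95 / 6000) ≈ 0.3 points under the null and √(0.9 × 0.1 / 6000) ≈ 0.4 points for power. Each row compares two models on the same data.

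**4. Reading the table.** The comparison that bears on the point is across a row. Power falls down the columns mainly because the conditional treatment effect is held fixed while the age effect grows, which shrinks the difference in proportions. That fall is not the cost of omitting age.

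The mechanism shows most clearly at an odds ratio of 4. Mean estimate over mean standard error is 0.500 / 0.164 = 3.05 without age and 0.557 / 0.174 = 3.21 with it (ratios from unrounded values). Under the null, the model standard error over the empirical SD is 0.165 / 0.166 = 0.99 without age and 0.174 / 0.181 = 0.96 with it. So the model without age is the more conservative of the two. Both sit at or above 5% because about 40 fixed site terms make the Wald test slightly liberal.

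**The case against.** The strongest objection is that Section 13.6 only summarises a SAP still to be written, and does not say that no other covariate will be used. The SAP may well add age. This does not remove the mismatch. Section 13.6 names the covariates model by model and keeps one stratification factor while dropping the other, so a SAP that follows it inherits the gap and one that adds age departs from it.

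A second objection is that the age association is only assumed. That stands: the protocol gives none, and with no association the gain is nil. Eruption and shedding of teeth could also act in opposite directions, so one linear term need not capture age. For attitude scales such as chance control or regret, nothing in the protocol shows that age predicts the outcome given its baseline.

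Three stronger readings are tempting and are not supported.

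- **A reader might infer that the primary test has a true type I error below 5%.** The simulation above gave 5.1% to 6.2% without age. Another, with 2,000 runs per scenario and much stronger effects of continuous age, gave 4.7%, 4.8% and 4.0%. Its Monte Carlo standard error is about 0.5 points, so the first two cannot be told from 5%, and the third arose at the most extreme age effect. Only conservatism relative to the age-adjusted model is supported.
- **A reader might infer that the trial is underpowered.** With the proportions held at 56% v 44%, power without age stayed between 92.8% and 93.6% for age log odds ratios of 0 to 0.9 per SD (2,000 runs per cell). Gains of 1 to 4 points did appear with log odds ratios of 0.4 to 0.9 per SD. If ages are uniform over five years, the SD is 5/√12 = 1.44 years, and these imply odds ratios of about 4 to 23 between youngest and oldest, beyond what the protocol can support.
- **A reader might call the odds ratio without age biased.** Its smaller size is non-collapsibility: it conditions on fewer covariates and so targets a different quantity.

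**Conclusion.** The mismatch is certain on the text: age stratifies the randomisation and is in none of the stated main models. The direction of its effect is also clear. If age predicts the outcome beyond site and baseline, the stated test is conservative relative to the age-adjusted one and loses power.

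The size is small. The loss is 0 to about 2 percentage points over assumed age-band odds ratios of 1 to 4, with rejection under the null at most about 0.5 points lower than in the age-adjusted model. These figures rest on the assumed age bands, age effect, site variation and baseline-caries effect set out above. The validity of the comparison, the planned 90% power and the total of 908 all stand. The point is worth acting on because the change is nearly free and affects the primary analysis.

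**What to change.** In Section 13.6, add age at randomisation to the primary logistic model and the count models alongside site and baseline caries, either in the bands used for stratification or as a continuous term. If it is continuous, the SAP should allow for a non-linear effect. Add it to the parent-reported models as well, for consistency with the stratified design. If age is left out on purpose, state the reason.

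Make the change before any comparative analysis, so that it cannot look driven by the data. It costs one or a few degrees of freedom and a change of wording. No extra children, visits or data are needed, because age is already collected on every child before randomisation.

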# 5 **INTRODUCTION**

# 5.1 Background

Child dental caries continues to be a problem in the UK despite considered efforts to ameliorate it; with a higher prevalence in deprived communities reflecting the social determinants of health (Public Health England, 2017). Public Health England's 2015 survey of 5-year-old children found 25% had experienced tooth decay, having 3 or 4 teeth affected. In the slightly later 2017 survey, 23% of 5-year-old children had tooth decay and those from deprived backgrounds had higher levels of decay (34%) than those who were least deprived (14%), a finding that appears to have changed little in between surveys (Public Health England, 2019). Prevention of child dental caries is a policy priority across the UK while dental extraction is the leading cause of hospital admission for children aged 5-9 years (Goodwin et al., 2015b). Dental caries that are left untreated in children can develop into a serious health condition and may result in admission to hospital for tooth extraction under a general anaesthetic, which may be the child's first experience of dental treatment. Other problems include insomnia, pain and days lost to school so its impact can be significant for the family (Goodwin et al., 2015b, Goodwin et al., 2015a).

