# 6.2 Outcomes

Outcome	Timing of measurement	Method of measurement	Objective	
Primary outcome	Primary outcome			
Caries experience (measured at dentinal level) at 24 months post- randomisation in any tooth which was caries free or unerupted at baseline	Baseline and 24 months (+/-3 months post randomisation).	Dental status examination to national standards as used in UK Dental Epidemiology Surveys of Child Dental Health	1, 8, 10, 11	
Secondary outcome(s)				
Number of teeth (caries free or unerupted at baseline) with caries experience into dentine 24 months post-randomisation.	Baseline and 24 months (+/-3 months post randomisation).	Dental status examination to national standards as used in UK Dental Epidemiology Surveys of Child Dental Health	2, 8	

 
Parent reported attitudes to child oral health behaviours (seven subscales)
 
Parental efficacy in relation to child toothbrushing
 
Importance and intention to brush child's teeth
 
Parental efficacy in relation to controlling child sugar snacking
 
	Baseline, 12 months and 24 months (+/- 3 months post randomisation).	Parent reported Oral Health Behaviours and Regret/Relief Questionnaire (OHB-RRQ)	2,8, 10, 11	

 
Importance and intention to control child sugar snacking
 
Perceived seriousness of tooth decay in children
 
Chance control – decay occurs by chance
 
Regret/Relief regarding child oral health behaviours
 
			

 
Parent reported child oral health behaviours (four measures)
 
Level of toothbrushing
 
Sweets consumption
 
Sugary drinks consumption
 
Dental attendance
 
	Baseline, 12 months and 24 months (+/- 3 months post randomisation).	Parent reported Oral Health Behaviours and Regret/Relief Questionnaire (OHB-RRQ)	2, 8
Episodes of dental pain	12 months and 24 months (+/- 3 months post randomisation).	From child dental treatment records of episodes of dental pain.	2
Number of filled teeth (caries free or unerupted at baseline) 24 months post randomisation	Baseline and 24 months (+/-3 months post randomisation).	Dental status examination to national standards as used in UK Dental Epidemiology Surveys of Child	2
Number of extracted teeth (caries free or unerupted at baseline) 24 months post randomisation	Baseline and 24 months (+/- 3 months post randomisation).	Dental status examination to national standards as used in UK Dental Epidemiology Surveys of Child	2
Economic outcomes			

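### The secondary tooth counts are assigned Poisson regression with no allowance for overdispersion, which clustering of affected teeth within children makes likely

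*Protocol*

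**What the plan says.** Protocol Section 13.6 names the model: "Count outcomes such as number of teeth developing caries, number of fillings and number of extractions will be compared using Poisson regression". Site and baseline caries are the covariates. It mentions no dispersion check, scaled or robust standard error, or alternative count model. The same section says "A full statistical analysis plan (SAP) will be written prior to the conduct of any comparative analysis of the treatment arms" and presents its content as the main features of that plan.

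The outcomes concerned are secondary. The first listed in Section 6.2 is "Number of teeth (caries free or unerupted at baseline) with caries experience into dentine 24 months post-randomisation"; the numbers of filled and extracted teeth are listed there too. The primary outcome is binary and is analysed by logistic regression.

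The protocol gives no mean, standard deviation or dispersion for any of these counts in the trial population. Its related figures are:

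- Section 5.1, survey of 5-year-olds: "found 25% had experienced tooth decay, having 3 or 4 teeth affected".
- Section 13.2.1, earlier trial in secondary care: "62% of children in the control group developed new caries, compared to 44% in the test group".
- Section 13.2.1, same trial: "The children in the sample achieved had a median of 5 teeth extracted".
- Section 5.2, same trial: 40% of control and 22% of intervention children had at least one restoration over two years.

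**The concern.** A Poisson model sets the variance equal to the mean. Caries shares its causes across a child's mouth, so a count of affected teeth tends to have many zeros and, among affected children, several teeth at once. The variance then exceeds the mean, and model-based Poisson standard errors are too small by the square root of the ratio. The rate ratio itself is still estimated properly, but its confidence interval is too narrow and its p-value too small.

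Section 13.2.1 gives fewer extractions and restorations, with lower NHS cost, as reasons for the trial. A spuriously significant rate ratio on one of these counts could be read as supporting evidence of clinical benefit.

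**Working it through.** **The plan's own figure.** The protocol states no variance or power for the counts, only a sample size for the binary primary outcome. It reproduces with 56% against 44% (a 12-point difference), two-sided 5% and 90% power: [1.96·√(2·0.5·0.5) + 1.2816·√(2·0.56·0.44)]² / 0.12² = 362.8, so 363 per group. Then 363/0.8 = 453.75, so 454 per group and 908 in total. The count model plays no part in it.

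**Notation.** Let p be the proportion of children affected, m the mean number of teeth per affected child, and φ the variance-to-mean ratio.

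- Minimum φ, if every affected child has exactly m teeth: (p·m² − p²m²)/(p·m) = m(1 − p). This needs no distributional assumption.
- Modest spread, with affected children following 1 + Poisson(m − 1): φ = (m − 1)/m + m(1 − p).
- Negative binomial: solve (1 + k·pm)^(−1/k) = 1 − p for k; then φ = 1 + k·pm.
- Actual error of a nominal 5% test with model-based errors: 2·[1 − Φ(1.96/√φ)].

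**Survey figures in Section 5.1** (p = 0.25, m = 3 to 4). The mean is 0.75 to 1.0. Poisson predicts e^(−0.75) = 47% to e^(−1.0) = 37% zeros, against 75% reported. Minimum φ is 3·0.75 = 2.25 to 4·0.75 = 3.0, which corresponds to 19 to 26% error.

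**Trial outcome.** The proportions p = 0.62 and 0.40 come from the earlier trial's control group (new caries and restorations respectively). The protocol does not give m, so it is an assumption, shown over a range.

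| p | m | φ, modest spread | error | φ, negative binomial | error |
|---|---|---|---|---|---|
| 0.62 | 1.56 | 0.95 | 4.5% | 1.00 (Poisson limit) | 5% |
| 0.62 | 2 | 1.26 | 8% | 1.61 | 12% |
| 0.62 | 3.5 | 2.04 | 17% | 4.24 | 34% |
| 0.40 | 2 | 1.70 | 13% | 2.31 | 20% |
| 0.40 | 3.5 | 2.81 | 24% | 5.83 | 42% |

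The 1.56 is the value at which Poisson reproduces 62% affected: −ln(0.38)/0.62 = 1.56. At 40% affected the corresponding value is −ln(0.60)/0.40 = 1.28.

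**Does covariate adjustment remove the problem?** Null data were simulated with the modest-spread shape, 363 children per arm, and adjustment for 40 sites and baseline caries (600 runs per row, Monte Carlo error 1 to 2 points).

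| p | m | model-based Poisson | robust errors |
|---|---|---|---|
| 0.62 | 1.56 | 2.8% | 4.8% |
| 0.62 | 2 | 7.2% | 4.7% |
| 0.62 | 3 | 14.0% | 6.0% |
| 0.62 | 3.5 | 17.3% | 7.0% |
| 0.40 | 1.5 | 9.0% | 6.0% |
| 0.40 | 2.5 | 19.7% | 6.7% |

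Adjustment barely reduces the inflation. Robust errors bring the test back to about 5 to 7%.

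**The case against.** The strongest reply is that Poisson regression with robust errors is still Poisson regression, so the sentence in Section 13.6 is not false. On this view the gap is only the variance estimator, a detail that the announced analysis plan may settle. That stands in part: it cannot be inferred that model-based errors will be used, and an unseen plan may already deal with this. But the protocol names this model as a main feature for the plan to carry forward. In the same section it expressly leaves imputation methods to the plan, and it does not do so for dispersion.

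The second reply is that the trial population differs from the survey. Section 8.1 requires at least one dentinal lesion, Section 8.2 excludes children needing referral for extractions, and Section 6.2 counts only teeth caries free or unerupted at baseline. The 75% zeros do not carry over. This stands, and it is why the result is given as a range that includes no inflation.

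A reader might infer something stronger from Section 5.1. A negative binomial with p = 0.25 and m = 3.5 gives φ of about 6.9, standard errors understated 2.6-fold and about 45% error. The documents do not support these as estimates for CHOICE. They rest on lifetime experience in a general population and on a distribution chosen to fit two summary figures. Nor does the median of 5 extractions settle the matter, since it describes extractions in children selected for needing them.

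**Conclusion.** The point holds as a likely problem, not a demonstrated one. The protocol fixes a count model whose variance assumption its own background figures make doubtful, and it provides no safeguard. With 40 to 62% of children affected and 2 to 3.5 teeth per affected child, model-based errors would give a type I error of roughly 8 to 24% with modest spread, and about 12 to 42% under a negative binomial shape. The result turns on teeth per affected child, which the protocol does not give.

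Only the secondary counts are touched. A reader should not conclude that the primary comparison or the 908 is in doubt. This should be fixed, but it does not threaten the trial's main conclusion.

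**What to change.** Amend the sentence in Section 13.6 so that all count outcomes are analysed by Poisson regression with robust (sandwich) standard errors, or by negative binomial regression, with the same covariates (site and baseline caries) and rate ratios reported. Carry the same wording into the statistical analysis plan before any comparative analysis, so that the choice is not made after seeing the data.

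The cost is one line of text. Sample size, design and data collection do not change. Intervals widen by about √φ: a factor of 1.12 at φ = 1.26 and 1.68 at φ = 2.81, which is the width the data would warrant. If the counts turn out not to be overdispersed, robust errors cost almost nothing.
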